## 9.0 STATISTICAL ANALYSIS

### 9.1 Sample Size Calculation

In the Phase 2, the VERU-111 treated group showed a 5.3% mortality rate compared to a 30% mortality rate in the Placebo group in the same patient population.

Approximately, 210 subjects are planned to be randomized at a 2:1 ratio into two treatment arms (140 subjects in the VERU-111 treated group and 70 subjects in the Placebo treated group). Randomization will be stratified by baseline WHO Ordinal Scale score of 4, 5 and 6 such that subjects with a WHO Ordinal Scale of 4, 5 and 6 at baseline will be approximately equally distributed between the treatment groups. Assuming a rate of mortality of 5% in the VERU-111 treated group and 25% in the Placebo treated group, the above sample sizes will yield 95% confidence interval of [-0.308, -0.092] for the risk difference between treatment groups. Other scenarios are shown in the table below.

$$\text{Confidence interval} = (p_1 - p_2) \pm z^* \sqrt{(p_1(1-p_1)/n_1 + p_2(1-p_2)/n_2)}$$

where:

- $p_1, p_2$ : sample 1 proportion, sample 2 proportion
- $z$ : the z-critical value based on the confidence level
- $n_1, n_2$ : sample 1 size, sample 2 size

Table of Alternative 95% Confidence intervals for the difference between Treatment Groups:  
 Mortality at Day 60

VERU-111	Placebo	Difference	LOWER 95% CI	UPPER 95% CI
0.05	0.15	-0.1	-0.191107629	-0.008892371
0.05	0.2	-0.15	-0.250420118	-0.049579882
0.05	0.25	-0.2	-0.307672652	-0.092327348
0.05	0.3	-0.25	-0.363261644	-0.136738356
0.1	0.15	-0.05	-0.147297482	0.047297482
0.1	0.2	-0.1	-0.206067903	0.006067903
0.1	0.25	-0.15	-0.262958399	-0.037041601
0.1	0.3	-0.2	-0.318297929	-0.081702071
0.15	0.15	0	-0.102449012	0.102449012
0.15	0.2	-0.05	-0.160812454	0.060812454
0.15	0.25	-0.1	-0.21742487	0.01742487
0.15	0.3	-0.15	-0.27256998	-0.02743002

With significance level  $\alpha=0.05$ , and a 2:1 ratio of enrollment into the VERU-111 and Placebo arms respectively, the sample size is adequate to achieve  $>92\%$  power assuming the treatment estimates stated above.

NOTE: The IDMC will monitor efficacy and safety and may make a recommendation to stop the study based on treatment success according to the statistical analysis plan and IDMC charter for this study.

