### 9.4.2 Secondary Analyses of the Primary Endpoint

The primary endpoint, mortality rate, will also be assessed in the subset of mITT patients.

To obtain risk differences between treatment groups, the same analysis as described above will be fitted except identity link function will be used.

Additionally, mortality rates will be summarized using Kaplan-Meier (KM) survival curves and equality of treatment groups will be tested using log-rank test. Hazard ratios will be calculated using the Cox proportional hazards model including terms for treatment, study site, gender, remdesivir use (No/Yes), dexamethasone use (No/Yes) and WHO Ordinal Scale for Clinical Improvement at baseline. Any subjects that are lost to follow-up or terminated early prior to death will be censored at the day of their last observed assessment or last captured event.

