6.11 Efficacy Analyses

All statistical tests will be performed using a two-tailed 5% overall significance level, unless otherwise stated. All comparisons between treatments will be reported with 95% confidence intervals for the difference.

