(no/yes, populated as ‘no’ for subjects who were not discharged from the hospital prior to withdrawing from the study before Day 60), DISCONT is whether subject discontinued treatment early (no/yes), REMDESIVIR is the use of remdesivir at baseline (no/yes), DEXAMETHASONE is the use of dexamethasone at baseline (no/yes) and WHOSTRATA is the WHO Ordinal Scale strata used in randomization. If the imputation model does not converge when both DISCHARGE and DISCONT variables are included then will be checked if either of them alone can be included in the model. If model converges with DISCHARGE or DISCONT alone but the model with both DISCHARGE and DISCONT does not converge, then imputation model will include only DISCHARGE.

The imputed data sets will be analyzed separately for each imputation using the logistic regression model. If all subjects have the mortality status at Day 60 then the imputation part above will not be used and observed data will be analyzed as such. Example SAS code for logistic regression is as follows:

```
proc logistic data=imputed1 order=internal descending;
by _imputation_;
class imputedresponse treatment sex site remdesivir dexamethasone whostrata
  / param=glm;
model imputedresponse = treatment sex site remdesivir dexamethasone whostrata
  / clodds=both firth;
estimate 'Treatment A vs. Treatment B' treatment 1 -1 / cl e exp;
lsmeans treatment / cl exp diff;
ods output modelanova=imputed_modelanova1
  lsmeans=imputed_lsmeans1
  diffs=imputed_diffs1
  parameterestimates=imputed_parmest1;
run;
```

If there are enough deaths to perform analysis without FIRTH option then it might be dropped out. Note that variable _IMPUTATION_ identifies each of the imputations created by PROC MI.

Finally, results from individual imputations are pooled via Rubin’s rules using PROC MIANALYZE. Example SAS code for pooling log(odds) for each treatment group is as follows:

```
proc mianalyze data=imputed_lsmeans1;
by trt01pn;
modeleffects estimate;
stderr stderr;
ods output parameterestimates=combined_odds1;
```

run;

Example SAS code for pooling log(odds ratio) for each treatment group is as follows:

```
proc mianalyze data=imputed_diffs1;
  modeleffects estimate;
  stderr stderr;
  ods output parameterestimates=combined_diffs1;
run;
```

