6.11.3 Secondary Analyses for the Primary Endpoint

The primary endpoint, mortality rate at Day 60, will also be assessed in the subset of mITT patients and Safety Analysis Set (all treated subjects).

Additionally, similar analysis to primary analysis will be performed in subgroups for region, standard of care, WHO Ordinal Scale at baseline and vaccination status.

To obtain risk differences between treatment groups, the same analysis as described above for primary efficacy analysis will be performed except identity link function will be used. Example SAS code is as follows:

```
proc genmod data=a order=internal;
class treatment sex site remdesivir dexamethasone whostrata;
model response=treatment sex site remdesivir dexamethasone whostrata
  / type3 dist=bin link=identity;
lsmeans treatment / e diff exp cl;
run;
```

Additionally, mortality rates will be summarized using Kaplan-Meier (KM) survival curves and equality of treatment groups will be tested using log-rank test. Hazard ratios will be calculated using the Cox proportional hazards model including terms for treatment, gender, study site (or country or region), remdesivir use (No/Yes), dexamethasone use (No/Yes) and WHO Ordinal Scale strata used in randomization. Any subjects for whom survival status is not available at day 60 will be censored at the day of their last observed assessment or last captured event.

Example SAS code for log-rank test is as follows:

```
proc lifetest data=XXX outsurv=surv1
  plots=survival(atrisk=0 to 60 by 1);
time time*cens(1);
strata treatment;
run;
```

Example SAS code for proportional hazards model is as follows:

```
proc phreg data=XXX;
class treatment sex site remdesivir dexamethasone whostrata;
model time*cens(1)=treatment sex site remdesivir dexamethasone
  whostrata;
```

Controlled Quality Management Document		
	Sponsor:	Veru Inc.
	Protocol Number:	V3011902

```
hazardratio treatment;  
assess ph / resample seed=1234;  
run;
```

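### The Cox model defaults to study site as an unpenalised fixed factor; with some 20 or more sites on about 25 deaths, a true benefit would tend to be overstated and the 95% interval would under-cover

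*SAP*

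**What the plan says.** The sentence in SAP 6.11.3 that defines the model reads "Hazard ratios will be calculated using the Cox proportional hazards model including terms for treatment, gender, study site (or country or region"; the bracket closes there and the remaining covariates follow. So three geographic terms are permitted. No rule for choosing among them is given.

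The PROC PHREG step below it is labelled as example code. It lists site in the CLASS statement and fits "model time*cens(1)=treatment sex site remdesivir dexamethasone" plus the WHO strata. It has no Firth option, no site stratification and no random effect.

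Protocol 9.4.2 offers no alternative to site: "Hazard ratios will be calculated using the Cox proportional hazards model including terms for treatment, study site, gender".

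The example code for the primary logistic model in SAP 6.11.1 does carry the Firth option, with a proviso: "If there are enough deaths to perform analysis without FIRTH option then it might be dropped out". No threshold is given for enough deaths.

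The SAP's amendment table explains the alternatives. Version 2.0 admitted country in case a model failed to converge. Version 4.0 admitted region because some countries had very few subjects and fitting might be difficult. Both entries list section 6.11.3.

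**The concern.** A site with no deaths has no finite maximum-likelihood coefficient in a Cox model. Its estimate runs to minus infinity, and its subjects then carry no weight in the treatment comparison. The other site effects are estimated from very few deaths each. When treatment has a real effect, fitting many such nuisance parameters pushes its estimate away from 1 and makes the model-based standard error smaller than the true sampling spread.

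The stated reason for moving to country or region does not catch this. The site coefficients diverge, but the treatment estimate nearly always stays finite and looks plausible. The default could therefore print a biased hazard ratio without anything in the plan requiring a switch. With no rule, the geographic term could also be chosen after the results are known.

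At stake is the mortality hazard ratio and its interval, which have their own planned ITT table (14.2.1.10).

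**Working it through.** **Inputs from the documents**
- Arm sizes, Protocol 9.1: "140 subjects in the VERU-111 treated group and 70 subjects in the Placebo treated group".
- Planning rates, Protocol 9.1: "Assuming a rate of mortality of 5% in the VERU-111 treated group and 25% in the Placebo treated group".
- Test level, SAP 6.11: "All statistical tests will be performed using a two-tailed 5% overall significance level, unless otherwise stated".

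**Assumptions (not in the documents)**
- 10, 20, 40 or 60 sites of uneven size.
- Region with four levels.
- Between-site SD of 0.6 on the log-hazard scale.
- Baseline WHO mix of 45/45/10%.

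**1. Reproduce the planning figure.** Protocol 9.1 says "the above sample sizes will yield 95% confidence interval of [-0.308, -0.092] for the risk difference between treatment groups". Its formula gives -0.20 ± 1.96 × √(0.05×0.95/140 + 0.25×0.75/70) = -0.20 ± 1.96 × 0.0549 = [-0.308, -0.092]. This matches.

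**2. Expected deaths.** 140×0.05 + 70×0.25 = 7 + 17.5 = 24.5. Across the protocol's scenario table the range is 17.5 (5% vs 15%) to 42 (15% vs 30%).

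**3. Deaths per parameter.** Treatment, sex, remdesivir and dexamethasone use one parameter each, the WHO strata two, and K sites K-1, so the total is 6 + (K-1).
- 4 levels: 24.5/9 = 2.7
- 10 sites: 24.5/15 = 1.6
- 20 sites: 24.5/25 = 0.98
- 40 sites: 24.5/45 = 0.54
- 60 sites: 24.5/65 = 0.38

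**4. True hazard ratio at the planning rates.** Under proportional hazards, ln(0.95)/ln(0.75) = 0.0513/0.2877 = 0.178.

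**5. Simulation with a true effect.** 1,000 trials per row, 210 subjects, 2:1 blocks within WHO strata, daily death times to Day 60, Breslow ties, Wald intervals. Entries are geometric mean hazard ratio / coverage of the 95% interval.

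| Sites | Site, no penalty | Model SE ÷ sampling SD (site, no penalty) | Site with Firth | Four-level region, no penalty |
|---|---|---|---|---|
| 10 | 0.149 / 94.6% | 0.91 | 0.161 / 95.4% | 0.165 / 94.9% |
| 20 | 0.131 / 92.8% | 0.83 | 0.148 / 95.0% | 0.165 / 95.5% |
| 40 | 0.113 / 89.1% | 0.80 | 0.137 / 93.7% | 0.178 / 96.1% |
| 60 | 0.079 / 80.0% | 0.64 | 0.105 / 90.5% | 0.166 / 94.8% |

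The Monte Carlo error of coverage is about 0.7 points near 95%. With no geographic term the hazard ratio was 0.172-0.185 and coverage 95.1-95.8%. The unpenalised treatment estimate failed to be finite in 1 of 999 trials with 40 sites and 6 of 1,000 with 60; these were left out.

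**6. Other runs.** Three further sets of simulations, one with a site SD of 0.5 and 600 trials and one with only 300 trials, gave:
- 20 sites: 0.138 / 91.0%, 0.133 / 93.3% and 0.140 / 94%.
- 40 sites: 0.114 / 85.8%, 0.111 / 84.8% and 0.123 / 87%.
- Subjects at zero-death sites (two of the three sets): 23-25% with 20 sites and 40-42% with 40.
- Region plus Firth: hazard ratios 0.162-0.185, coverage 95-97%.

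**7. Simulation with no effect.** At 11.7% mortality in both arms (24.5/210), the site-adjusted geometric mean hazard ratio was 1.03-1.05, the same as without site. Two-sided rejection at a nominal 5% was 6.0%, 7.3%, 7.4% and 10.2% for 10, 20, 40 and 60 sites. With four-level region it was 3.9-5.5%. Other runs with 40 sites gave 5.7%, 9.0% and 9.8%.

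**The case against.** The strongest reply is that the plan already permits the main remedy. The defining text allows region, the code is only an example, and section 6.11.3 was amended for this kind of difficulty. A four-level region term without a penalty shows little bias and nominal coverage. That stands. It is why the point concerns the default and the missing rule, and is not a claim that the analysis must go wrong. An analyst who notices diverging site coefficients may well switch, but nothing in the text requires it.

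Four stronger readings are tempting, and the material does not support them:
- **That the hazard ratio is certainly exaggerated.** The size depends on the number of sites, which neither document gives. With 10 sites coverage is nominal and the shift is smaller (0.149 against 0.178).
- **That the interval is simply too narrow.** Adjusting for site widens it: the mean standard error is 0.49 to 0.71, against about 0.46 without site. The fault is that it does not widen enough.
- **That a benefit would appear where none exists.** With no true effect the estimate is not shifted; only the error rate may rise.
- **That the missing Firth option is the main cause.** Site with Firth still gives 0.105 and 90.5% coverage with 60 sites, whereas region without Firth removes most of the bias. The contrast with the primary model is also softer than it looks, because the SAP allows Firth to be dropped there.

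It is also fair to say that the consequence is limited. The confirmatory test is the logistic model, the log-rank code has no site term, and the Cox test has no place in the multiplicity scheme of SAP 6.11.7.

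**Conclusion.** The concern holds in conditional form. If the coded default is used with an assumed 20 or more sites on about 24.5 deaths, a true hazard ratio of 0.178 would tend to be reported as about 0.13-0.14 with 20 sites and 0.11-0.12 with 40. At 0.113 that is an apparent hazard reduction of about 89%, where the truth is 82%. Coverage falls to about 91-94% and 85-89%. With no effect the false-positive rate with 40 sites may be about 6-10%, and the simulations disagree within that range.

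These sizes rest on the planning mortality rates and on assumed site numbers, site sizes and between-site variation. A reader might infer that the trial's main mortality conclusion is at risk. It is not: this is a supportive analysis that cannot alter the primary logistic test or the log-rank test. The change is still worth making, because it is cheap and the stated reasons for leaving site would seldom be triggered.

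**What to change.** In SAP 6.11.3:
- Name region, in place of the three-way choice, as the geographic term in the Cox text, and list its levels. The SAP text does not list them, and four were assumed here.
- In the PROC PHREG example, replace site with region in the CLASS and MODEL statements and add the Firth option to the MODEL statement. Region does most of the work; Firth adds a small further correction.
- Record the departure from Protocol 9.4.2, which names study site, in SAP section 9.

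The cost is one variable, one option, a sentence of text and one entry in the list of changes. There are two drawbacks. The reported hazard ratio will be less extreme. The Cox geographic term may also differ from the one in the primary model if that model keeps site, and the SAP should say so.

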6.11.4 Exploratory Analysis for the Primary Endpoint

Not applicable.

6.11.5 Secondary Efficacy Analyses

6.11.5.1 The proportion of subjects that are alive without respiratory failure at Day 15, Day 22, and Day 29.

This analysis will compare subjects that are alive without respiratory failure on the visit (responder) to subjects who died before the visit or had respiratory failure (non-responder) on the visit.

Responders are subjects who are alive and have Grade 0-4 on the WHO Ordinal Scale for Clinical Improvement on the visit. If subject was discharged from the hospital prior to the visit and WHO Ordinal Scale for Clinical Improvement is not collected at the specific visit then the last available observation before or at the time of discharge will be used. If subject's vital status is not known then missing information will be imputed using multiple imputation.

Non-responders are subjects who died before the visit or has Grade 5, 6, 7, or 8 on the WHO Ordinal Scale for Clinical Improvement on the visit.

The number and percentage of responders will be summarized by treatment group and visit.

Responders will be analyzed using the same methodology as for the primary endpoint (separate analysis will be performed for each visit):

- Multiple imputation + logistic regression model

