#### **8.4 Day 2 through Day 21 or day of discharge from the hospital (whichever comes first)**

The following assessments will be conducted on each of Day 2 to Day 21 or up to the day of discharge from the hospital, whichever comes first:

1. Vital signs (temperature/pulse/supine, if possible, blood pressure)
2. Record the usage of any concomitant medications and ongoing treatments. This should include the following:
  - a. Documentation of the standard of care
  - b. The clinical rationale for initiation of mechanical ventilation, if necessary
  - c. Documentation of supportive measures for ARDS (e.g., proning, paralytics, etc.)
  - d. Care decisions that are based on limitations of resources at the clinical site
3. Adverse events
4. Dose study drug
5. At the time of discharge from the hospital, patients should be advised to use refrain from prolonged exposure to the sun or use at least SPF 50 on all exposed skin and protective clothing during prolonged sun exposure until the Day 60 adverse event assessment.

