## 9.5 Secondary Endpoint

Primary analysis of secondary endpoints will be performed on the ITT analysis set and the ITT data scope regardless of patient's use of rescue medications, protocol violations or investigational product discontinuation consistent with the treatment policy strategy.

Full details for the handling of missing data, and consideration of subjects that die during the study for those endpoints that do not directly incorporate death, will be included in the Statistical Analysis Plan.

### 9.5.1 Proportion of patients alive and free of respiratory failure at Day 29, Day 15 and Day 22

Respiratory failure is defined as endotracheal intubation and mechanical ventilation, extracorporeal membrane oxygenation, high-flow nasal cannula oxygen delivery, noninvasive positive pressure ventilation, clinical diagnosis of respiratory failure with initiation of none of these measures only when clinical decision making is driven solely by resource limitation.

This analysis will compare the percentage of subjects that are alive without respiratory failure (responder) on Day 29 and on Day 15 and on Day 22.

Proportion of subjects alive and free of respiratory failure will be analyzed separately at each timepoint using the same logistic regression methodology as primary endpoint ([section 9.4.1](#)).

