2.2 Secondary Objectives

The secondary objectives/endpoints on this study are:

Controlled Quality Management Document		
	Sponsor: Veru Inc.	Protocol Number: V3011902
STATISTICAL ANALYSIS PLAN. PHASE 2-3-4		

1. The proportion of subjects that are alive without respiratory failure at Day 15, Day 22, and Day 29. Day 29 is the key secondary endpoint. Respiratory failure is defined as endotracheal intubation and mechanical ventilation, extracorporeal membrane oxygenation, high-flow nasal cannula oxygen delivery, noninvasive positive pressure ventilation, clinical diagnosis of respiratory failure with initiation of none of these measures only when clinical decision making is driven solely by resource limitation
2. Days in Intensive Care Unit (ICU)
3. WHO Ordinal Scale for Clinical Improvement change from baseline to Day 15, Day 22, and Day 29.

Patient State	Descriptor	Score
Uninfected	No clinical or virological evidence of infection	0
Ambulatory	No limitation of activities	1
	Limitation of activities	2
Hospitalized, Mild disease	Hospitalized, no oxygen therapy	3
	Oxygen by mask or nasal prongs	4
Hospitalized, Severe disease	Non-invasive ventilation or high-flow oxygen	5
	Intubation and mechanical ventilation	6
	Ventilation + additional organ support – pressors, Renal Replacement Therapy (RRT), Extracorporeal Membrane Oxygenation (ECMO)	7
Death	Death	8

4. Days on mechanical ventilation
5. Days in hospital

Controlled Quality Management Document		
	Sponsor: Veru Inc.	
	Protocol Number: V3011902	
STATISTICAL ANALYSIS PLAN. PHASE 2-3-4		

6. Proportion of subjects that die on study at Day 15, Day 22, and Day 29.
7. Change from baseline in viral load (baseline to Day 9).

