3.2 Secondary Endpoints

The secondary endpoints on this study are:

1. The proportion of subjects that are alive without respiratory failure at Day 15, Day 22, and Day 29. Day 29 is the key secondary endpoint. Respiratory failure is defined as endotracheal intubation and mechanical ventilation, extracorporeal membrane oxygenation, high-flow nasal cannula oxygen delivery, noninvasive positive pressure ventilation, clinical diagnosis of respiratory failure with initiation of none of these measures only when clinical decision making is driven solely by resource limitation.
2. Days in ICU
3. WHO Ordinal Scale for Clinical Improvement change from baseline to Day 15, Day 22, and Day 29
4. Days on mechanical ventilation
5. Days in hospital
6. Proportion of subjects that die on study at Day 15, Day 22, and Day 29.
7. Change from baseline in viral load (baseline to Day 9)

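### SAP 6.11.5.1 scores the key secondary endpoint by WHO score alone, so resource-limited respiratory failure, a failure under the endpoint definition, counts as success in a living subject

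*SAP*

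**What the plan says.** Both documents define respiratory failure in the same way (Protocol 2.0, 4.2, 5.3.2 and 9.5.1; SAP 2.2 and 3.2). Four components are supports the subject receives: intubation with mechanical ventilation, ECMO, high-flow nasal oxygen, and non-invasive positive pressure ventilation. The fifth is "clinical diagnosis of respiratory failure with initiation of none of these measures only when clinical decision making is driven solely by resource limitation". On the three visit days the SAP states: "Day 29 is the key secondary endpoint".

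SAP 6.11.5.1 opens by comparing responders with "subjects who died before the visit or had respiratory failure (non-responder) on the visit". It then fixes the classification by score. For success: "Responders are subjects who are alive and have Grade 0-4 on the WHO Ordinal Scale for Clinical Improvement on the visit". For failure: "Non-responders are subjects who died before the visit or has Grade 5, 6, 7, or 8 on the WHO Ordinal Scale". Neither sentence mentions the fifth component.

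Protocol 8.4, item 2d, asks sites to document the following on Days 2 to 21 or until discharge: "Care decisions that are based on limitations of resources at the clinical site". SAP 6.11.5.1 does not refer to this record.

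**The concern.** The WHO scale records the support a subject is getting, not the support the subject needs. The fifth component covers subjects whose need was recognised but not met. A rule built only on the score cannot see them, so the analysed endpoint is narrower than the one both documents define. At stake is whether the Day 29 result means what its label says. If such cases occur, responder rates are overstated and the result depends partly on what equipment a site had free.

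**Working it through.** **Step 1: set the definition beside the scoring rule.** The WHO descriptors are from SAP 2.2.

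| Component of respiratory failure | WHO score in a living subject | Class under SAP 6.11.5.1 |
|---|---|---|
| High-flow nasal oxygen, or non-invasive positive pressure ventilation | 5, "Non-invasive ventilation or high-flow oxygen" | Non-responder |
| Intubation and mechanical ventilation | 6 | Non-responder |
| ECMO | 7 | Non-responder |
| Clinical diagnosis, no measure started, solely for lack of resources | 4 (mask or nasal-prong oxygen) or 3 (no oxygen) | **Responder** |

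A subject meets the fifth component only if none of the listed measures was started, and those measures are what scores 5 to 7 describe. The component therefore cannot register as failure in anyone alive at the visit. This follows from the definitions and needs no assumed rate. A subject who died before the visit is a non-responder in any case.

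**Step 2: look for a cure elsewhere.** Protocol 9.5.1 carries the fifth component ("initiation of none of these measures only when clinical decision making is driven solely by resource limitation") and does not map the endpoint to the WHO scale. The visible text of SAP section 9 lists three changes from the protocol: the stratification, the WHO score analysis, and the Holm procedure. This change is not among them.

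**Step 3: size.** The documents give no sample size, power or expected rate for this endpoint. The interval and power in Protocol 9.1 concern Day 60 mortality and do not bear on it. For illustration, the inputs are:

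- Phase 2 Day 29 failure rates from Protocol 3.3: placebo 30.0%, VERU-111 10.5%. The quoted 65% reduction reproduces: 1 − 10.5/30.0 = 0.65.
- Planned arms from Protocol 9.1: 70 placebo, 140 VERU-111.
- Share of failures missed, m: not in the documents; 0 to 20% assumed.

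Observed failure rate = true rate × (1 − m). Odds ratio = [pV/(1 − pV)] / [pP/(1 − pP)], where V is VERU-111 and P is placebo.

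| Share missed, placebo / VERU-111 | Failure rate, placebo / VERU-111 | Difference (points) | Odds ratio |
|---|---|---|---|
| 0 / 0 | 30.0% / 10.5% | 19.5 | 0.274 |
| 5% / 5% | 28.5% / 9.975% | 18.525 | 0.278 |
| 10% / 10% | 27.0% / 9.45% | 17.55 | 0.282 |
| 20% / 20% | 24.0% / 8.4% | 15.6 | 0.290 |
| 10% / 0 | 27.0% / 10.5% | 16.5 | 0.317 |
| 20% / 0 | 24.0% / 10.5% | 13.5 | 0.372 |
| 0 / 10% | 30.0% / 9.45% | 20.55 | 0.244 |
| 0 / 20% | 30.0% / 8.4% | 21.6 | 0.214 |

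Worked example at 10% in both arms: (0.0945/0.9055) / (0.27/0.73) = 0.1044/0.3699 = 0.282. In subjects this is 70 × 0.30 × 0.10 = 2.1 on placebo and 140 × 0.105 × 0.10 = 1.5 on VERU-111. Responder rates become 73.0% instead of 70.0% and 90.55% instead of 89.5%.

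The planned analysis is logistic regression, so the odds ratio is the relevant scale. Equal shares hardly move it; unequal shares move it in either direction.

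**The case against.** **The opening sentence may carry the full definition.** SAP 6.11.5.1 speaks of subjects who had respiratory failure, a term SAP 3.2 defines in full. That is a fair reading of the sentence, but the section then contradicts itself. The explicit score rule is the one likely to be programmed, so the text still needs correcting.

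**Cases may be rare or absent.** This stands. Subjects with WHO scores of 5 and 6 are eligible, so sites enrolling them had the equipment, although that does not show a device was free on a given day. A reader might infer that failures at hard-pressed sites are in fact being turned into successes. The documents do not show that any such case exists.

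**Direction and power.** A reader might also infer that the rule dilutes the treatment effect and costs appreciable power. That requires an assumed number of cases, and a large loss requires a higher miss share on placebo. The trial is double-blind, and nothing in the documents supports a difference between arms. The last two rows of the table show bias in favour of VERU-111.

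**Confirmatory weight.** SAP 6.11.7 reserves the Holm procedure for days in ICU and days on mechanical ventilation. The endpoint is labelled key secondary but has no alpha, so a power argument carries little weight.

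**Data.** It is tempting to say that item 2d already supplies what is needed. It records resource-limited care decisions, not a clinical diagnosis of respiratory failure. Nor are Days 22 and 29 without any source: Protocol 8.6 and 8.7 collect adverse events and ongoing treatments, though not item 2d by name.

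**Conclusion.** The mismatch is real and rests on the text alone: one of five components of the stated definition cannot count as failure in a living subject under the SAP's rule, and the visible SAP does not report this as a change. Its numerical effect is unknown and may be nil.

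If the Phase 2 Day 29 rates hold and up to 20% of failures are missed equally in both arms, the risk difference falls from 19.5 to at worst 15.6 points and the odds ratio moves from 0.274 to 0.290. Both the rates and the shares are assumptions. The documents do not say how Phase 2 scored resource-limited cases. They support neither a predicted direction of bias nor a stated loss of power. The point is worth correcting because the endpoint analysed should be the endpoint defined. Its confirmatory impact is limited.

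**What to change.** Add to the non-responder rule in SAP 6.11.5.1: *or a documented clinical diagnosis of respiratory failure at the visit with none of the listed measures started solely because of resource limitation, whatever the WHO score.* Restrict the responder rule to match.

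Classify blinded to treatment from existing records: the item 2d care-decision record, plus adverse event and concomitant treatment records for the diagnosis and for Days 22 and 29. Where the eCRF can still be changed, add one yes/no item at Days 15, 22 and 29 that captures both the diagnosis and the resource limitation. SAP version 5.0 describes its changes as clarifications made during output production, so a new item may no longer be practical, or may need retrospective collection or a protocol amendment.

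If the component cannot be ascertained, state death or WHO 5 to 8 as the operational definition and list it in SAP section 9 as a change from the protocol.

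The cost is one clause, one derivation flag and a small blinded data review, with a possibly slightly lower responder rate. If no case is found, the results do not change.
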